7.3 Lost to Follow-Up

N/A

STUDY ASSESSMENTS AND PROCEDURES

8.1 Endpoint and Other Non-Safety Assessments

The only assessment for this study will be one online survey which can be completed in approximately 10-20 minutes. The survey will collect demographics information, relationship status, infertility history, experience using the Mosie Kit and perceptions related to its use and safety.

8.2 Safety Assessment

Since there is no intervention there will be no safety assessments related to the survey however, questions about the perceived safety of using the Mosie Kit Syringe will be asked.

8.3 Adverse Events and Serious Adverse Events

This retrospective study does not expect there to be any adverse events reported due to participating in the survey. It does however ask questions about any infections that might have occurred during the prior 7 months. While these infections might be completely unrelated to using the Mosie syringe, the response will be evaluated and examined as a percentage of respondents and cycles. It is one of the goals of this study to find out if there might be any adverse events due to the use of the Mosie Kit.

Nonetheless, the definitions and classification for adverse events are outlined below.

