5 STUDY POPULATION

The study population will consist of all individuals who have purchased the Mosie Kit in the past 2-8 complete months prior to study initiation. All qualifying individuals will receive an invitation to participate. These individuals will typically be of child-bearing age, both females and males, and generally ages ranging 18-50 years old.

It is assumed that purchasing the Mosie Kit means the kit will be used as intended for at-home insemination. One of the inclusion criteria is to have previously used the kit. Therefore, the initial list of study participants will be drawn from people who have placed a purchase order within the prior 8 complete months; complete months are used with the expectation that the Mosie Kit would be used within the month post-purchase. If the study duration is expanded, additional potential participants will be invited who have purchased the kit at least 2 full months prior to being invited to participate in the study.

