5.1 Inclusion Criteria

In order to be included in the study, the following inclusion criteria will be used.

Inclusion Criteria:

- Provide implicit consent by filling out and submitting the survey.
- Used a Mosie Kit to conceive during at least one cycle.
- At least 18 years old.
- Has an active email on file (presumed or they would not have received an invitation to participate. This information will not be verified as there is a desire to keep the survey completely anonymous.)

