Analysis: Descriptive statistics surrounding the ease of use on a 5-point likert (very easy to very difficult) will be analyzed on five different aspects of use. Specifically, the steps of using the Mosie Kit (collecting a sperm sample, drawing up the sample in the Mosie syringe, inserting the syringe, and depositing the sperm at or near the cervix) and overall ease of use will be examined. Additionally questions related to use such as comfort, ease and safety of the process, enjoyable and intuitiveness of use (able to use it without instructions) will allow the user to rate their experience from Strongly agree to strongly disagree (5 point scale). The data will be plotted and examined as part of the analysis.

Secondary Hypothesis 2: The participants were able to use the Mosie Kit as instructed using the instructions contained in the kit. The alternative hypothesis is that the participants were not able to use the kit using the instructions contained in the kit.

Analysis: Descriptive analysis of perceived overall success rate will be analyzed. Additionally, descriptive analysis of the frequency of each expected behavior related to use of the kit will be examined.

Secondary Hypothesis 3: The participants reported they used the kit as intended, specifically, using it within 24 hours of initial signs of ovulation and again 24-48 hours after ovulation was confirmed or expected. The alternative hypothesis is that the participants report they did not use the kit as intended with respect to timing (within 24 hours of initial signs of ovulation and again 24-48 hours post ovulation).

Analysis: Frequency rates related to timing of insemination at all reported cycles will be analyzed. The data will be reported in both total number of attempts at each time point as well as percentage of attempts at each time point in comparison with total cycles where the Mosie Kit was used. T-tests will also be used in this analysis. Additionally,

amount of time lying after insemination and position of lying will be analysed using descriptive statistics and correlations with pregnancy rate.

Secondary Hypothesis 4: Participants reported they perceived the Mosie Kit to be a safe way to conceive. The alternative hypothesis is that participants did not perceive the Mosie Kit to be a safe way to conceive.

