Appendix A: Online Survey Tool and Consent Form (Google Form)

This section shows what the Google Form will look like to the study participant. These are the questions the participant will be asked.

The first page of the study contains the consent form and the question that confirms the participant's agreement to participate.

There is skip logic for certain sections. For example, if the participant selects one cycle of using Mosie, the information related to cycles 2-6 will be skipped. If the participant selects that she is pregnant the questions related to the pregnancy will be asked, otherwise they will be skipped. If a donor was used, the questions related to producing a sperm sample will be skipped.

Note: Final language and questions might be tweaked or revised at any time to increase clarity.

MOSIE-001 © 2020 Mosie Baby Page 38

[figure not shown]
This is the inclusion/exclusion form.

If Participant selected to not participate in the study, he/she will see this screen next. If the participant said he/she is not 18 or older or has not used Mosie this screen will be displayed.

[figure not shown]

Qualifying participants will continue the survey on this page.

[figure not shown]

[figure not shown]
	ch of these diagnoses or issues do you believe are contributing to your rtility? *
	Not applicable
	PCOS
	Endometriosis
	Low AMH or low ovarian reserve
	Low Sperm count
	Sperm motility issues
	Erectile Dysfunction
	Performance issues or sexual anxiety, or inability to orgasm with partner
	Vaginismus or vulvodynia
	Tilted Uterus
	Multiple uterus/cervix
	Unexplained infertility
	Have only one functioning fallopian tube
П	Other:

[figure not shown]
No other method	is attempted			
Male/Female into	ercourse			
IVI or syringe oth	ner than Mosie			
IUI				
Femara				
Clomid				
IVF				
Cervical Cap				
Other:				
	None	1	2	3 or more
How many pregnancies have you had?	0	0	0	0
pregnancies	0	0	0	0
pregnancies have you had? How many live births have you had? How many pregnancies have you had that were	0	0	0	0
pregnancies have you had? How many live births have you had? How many pregnancies have you had	0	0	0	0

[figure not shown]

[figure not shown]
	0	1	2	3+
24-48 hours prior to ovulation	0	0	0	0
within 24 hours of ovulation	0	0	0	0
24-48 hours after ovulation	0	0	0	0
48+ hours after ovulation	0	0	0	0
Did you use Mosie fo Yes No	or another cy	cle?		

[figure not shown]

[figure not shown]

[figure not shown]

[figure not shown]

Mosie Kit Survey

* Required

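### Section 8.3's infections-per-cycle figure divides a fixed 7-month count by one to six cycles of kit use, so it cannot be read as an infection risk per Mosie cycle

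*Combined protocol and SAP*

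**What the plan says.** Section 8.3 sets the numerator: "It does however ask questions about any infections that might have occurred during the prior 7 months". It grants that such infections may have nothing to do with the syringe, and then sets the denominators: "the response will be evaluated and examined as a percentage of respondents and cycles".

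Exposure is defined elsewhere. Section 5 states: "The study population will consist of all individuals who have purchased the Mosie Kit in the past 2-8 complete months prior to study initiation", with "the expectation that the Mosie Kit would be used within the month post-purchase". Section 5.1 requires only this much use: "Used a Mosie Kit to conceive during at least one cycle". Section 1.1 looks at up to six cycles, and Appendix A describes the matching skip logic: "if the participant selects one cycle of using Mosie, the information related to cycles 2-6 will be skipped".

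Section 8.3 does not say what a cycle is. Section 9.1 expresses timing of insemination "in comparison with total cycles where the Mosie Kit was used", and Appendix A uses the word in the same sense, so I read it as cycles of Mosie use.

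Three other places bear on the point. Section 8.3.4 speaks of past self-reported vaginal infections, gives no window, and says relatedness to the kit cannot be judged. Section 8.3.8 confines capture to events that go with use of the kit. Section 9.1, under Secondary Hypothesis 4, plans descriptive statistics for vaginal infection rates. No section dates infections, limits them to the time after first use, or defines time at risk per cycle.

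**The concern.** A rate per cycle is useful if the events counted could have arisen in the cycles counted. Here the numerator covers the same seven calendar months for everyone, while the denominator is however many cycles each person used. Two people with the same background infection risk and no kit effect then give different per-cycle values simply because one used the kit more often. For recent buyers, much of the recall period also falls before they owned a kit.

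Section 8.3 makes finding possible adverse events from the kit a goal of the study, and sections 10.1.3 and 10.1.11 foresee publication and marketing use of aggregate results. A per-cycle infection percentage would naturally be read as the risk of using the kit for one cycle. The survey is anonymous and taken once, so timing that is not asked for cannot be recovered later.

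**Working it through.** The documents give no infection rate, event count or time at risk, so there is no figure of the plan's own to reproduce. The check lines up the windows.

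**Inputs from the documents.** Recall window: 7 months (section 8.3). Months since purchase at Day 0, t: 2 to 8 (section 5). Cycles used, k: at least 1 (section 5.1), at most 6 (section 1.1, Appendix A). Collection may run to 90 days (section 10.1.2).

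**Assumptions.** First-time buyers. A 7-month prevalence p of 5, 10 or 20%, with one infection per person reporting. Purchases spread evenly over t = 2 to 8, with linearly rising or falling sales as alternatives. A 30.4-day month and a 28-day cycle.

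**Step 1: per-cycle figure with no kit effect.** Infections per respondent are p and cycles per respondent average k, so the figure is p/k.

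| p | k = 1 | k = 3 | k = 6 |
|---|---|---|---|
| 5% | 5.0% | 1.7% | 0.8% |
| 10% | 10.0% | 3.3% | 1.7% |
| 20% | 20.0% | 6.7% | 3.3% |

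The spread is sixfold whatever p is. The recall window relative to time in use is 7 × 30.4/(28k), which is 7.6 for one cycle, 2.53 for three and 1.27 for six. With no kit effect, the figure exceeds the background risk over one 28-day cycle by those factors.

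**Step 2: recall time before purchase, Day 0.** The share is max(0, 7 − t)/7.

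| t (months) | 2 | 3 | 4 | 5 | 6 | 7 | 8 |
|---|---|---|---|---|---|---|---|
| Share before purchase | 5/7 = 71% | 57% | 43% | 29% | 14% | 0 | 0 |

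Averages over t:
- Even purchases: (12.5/6)/7 = 2.083/7 = 29.8%.
- Sales rising to the latest month, density (8 − t)/18: 3.009/7 = 43.0%.
- Sales falling, density (t − 2)/18: 1.157/7 = 16.5%.
- Even purchases, first use a full month after purchase (the limit of the section 5 expectation): share before use (18/6)/7 = 42.9%, and 6/7 = 86% at t = 2.

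**Step 3: ownership outside the window.** The excess is max(0, t − 7).
- Day 0: at most 1 month. With even purchases, (0.5/6)/5 = 0.083/5 = 1.7% of owned time.
- Day 90, so t runs from 5 to 11: up to 4 months, and (8/6)/8 = 1.333/8 = 16.7% of owned time. The pre-purchase share falls to (2/6)/7 = 4.8%, before counting the newer buyers whom section 5 would then invite.

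Steps 2 and 3 are shares of calendar time, not measured bias.

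**The case against.** The strongest objection is that the infection question itself sits in a figure not shown. It may be tied to kit use, as section 8.3.8 would allow, and a percentage of cycles might mean cycles in which an infection occurred. This stands: a reader might infer that the survey has the fault, and the documents do not show that. If the question is tied to use, however, section 8.3 misdescribes it and still needs correcting.

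Second, the windows overlap a good deal. With even purchases at Day 0, about 70% of recall time follows purchase (100 − 29.8) and about 98% of owned time lies inside the window (100 − 1.7). A reader might infer that the count has no time in common with exposure; that would be too strong. But overlap in months does not repair a denominator counted in cycles.

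Third, the sixfold spread compares hypothetical samples. The study would produce a pooled figure, and sections 9.4.2 and 9.4.3 plan no comparison of infections by number of cycles. This also stands. The pooled figure still depends on mean cycles used, which the documents do not give.

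Fourth, a reader might infer that sections 8.3, 8.3.4 and 8.3.8 give three incompatible accounts. They do not. Section 8.3.4 names the infection type and offers no rival window, so it fits section 8.3. Only section 8.3.8 is in tension, and mildly, since section 8.3.1 counts events that accompany use whether or not they are judged related.

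Fifth, a reader might infer that this rate is all the study learns about infections. Appendix A also collects infection type and treatment, section 9.4.1 describes every question, and section 9.1 adds qualitative review of safety comments.

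Last, the analysis is descriptive, sections 8.3 and 8.3.4 disclaim attribution, and the endpoint in section 3 is perceived safety. That limits the consequences. It does not make numerator and denominator match.

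**Conclusion.** The point holds for the protocol text. The per-respondent percentage is sound as a 7-month period prevalence, provided that it is not presented as a rate during kit use. The per-cycle percentage, computed as section 8.3 reads, has no interpretation as risk per Mosie cycle: with no kit effect it is inversely proportional to the mean number of cycles. The 1/cycles behaviour needs no assumption about prevalence. The pre-purchase share does rest on assumptions: about 30% with even purchases, 17 to 43% with linearly falling or rising sales, first-time buyers only. Repeat buyers may have been exposed earlier.

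At Day 0 the error is mainly over-counting, which is the cautious direction for a safety signal. If collection runs to Day 90, missed time among the oldest buyers is added. No test, sample size or decision rule depends on the figure. It is worth changing because it bears on a stated safety goal and the correction is cheap.

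**What to change.** In section 8.3, define cycles as recorded Mosie cycles, and then do one of the following.

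- **(a)** Drop the per-cycle rate and label the per-respondent figure a 7-month period prevalence not tied to kit use. This needs no new data and works if the survey has already run. The only loss is a figure that could not be interpreted.
- **(b)** If the survey can still be changed, ask those reporting an infection whether it occurred before first use, in a recorded Mosie cycle (and which), or between or after cycles. Compute the per-cycle rate only from infections placed in a recorded cycle. Report between/after infections separately as a percentage of respondents; dividing them by cycles would bring the unequal-time problem back. The recall period must reach back to the first recorded cycle, or older cycles enter the denominator with no chance of contributing an event.

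Under either option, reconcile the capture window in section 8.3 with section 8.3.8.

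Option (b) costs one extra question for some respondents. Appendix A leaves room for it: "Final language and questions might be tweaked or revised at any time to increase clarity". It also brings recall error in timing, over up to about 8 months for first-time buyers at Day 0 and about 11 at Day 90. It does not establish causation. Under the Statement of Compliance, the protocol rewording needs IRB approval before use.

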8.3.1 Definition of an Adverse Event

This protocol uses the definition of adverse event from 21 CFR 312.32 (a): any untoward medical occurrence associated with the use of an intervention in humans, whether or not considered intervention-related. However, as a cross-sectional study, only retrospective information will be available if provided by the Participant.

8.3.2 Definition of Serious Adverse Events

According to the FDA a serious adverse event is one that results in death, disability, require and intervention to prevent a disability or permanent damage, birth defect or hospitalization. ER visits without hospitalization are individually evaluated for their severity to determine if they are a serious adverse event.

8.3.3 Classification of an Adverse Event

8.3.3.1. Severity of Event

For adverse events (AEs) not included in the protocol defined grading system, the following guidelines will be used to describe severity.

- **Mild** Events require minimal or no treatment and do not interfere with the participant's daily activities.
- **Moderate** Events result in a low level of inconvenience or concern with the therapeutic measures. Moderate events may cause some interference with functioning.
- **Severe** Events interrupt a participant's usual daily activity and may require systemic drug therapy or other treatment. Severe events are usually potentially life-threatening or incapacitating. Of note, the term "severe" does not necessarily equate to "serious".

8.3.3.2. Relationship to Study Intervention/Experimental Manipulation

All adverse events (AEs) will have their relationship to study procedures, including the intervention, assessed by an appropriately-trained clinician based on temporal relationship and his/her clinical judgment. The degree of certainty about causality will be graded using the categories below.

- Definitely Related There is clear evidence to suggest a causal relationship, and other possible contributing factors can be ruled out. The clinical event, including an abnormal laboratory test result, occurs in a plausible time relationship to study procedures administration and cannot be explained by concurrent disease or other drugs or chemicals. The response to withdrawal of the study procedures should be clinically plausible. The event must be pharmacologically or phenomenologically definitive.
- Probably Related There is evidence to suggest a causal relationship, and the
 influence of other factors is unlikely. The clinical event, including an abnormal
 laboratory test result, occurs within a reasonable time after administration of the
 study procedures, is unlikely to be attributed to concurrent disease or other drugs
 or chemicals, and follows a clinically reasonable response on withdrawal.
- Potentially Related There is some evidence to suggest a causal relationship (e.g., the event occurred within a reasonable time after administration of study procedures). However, other factors may have contributed to the event (e.g., the participant's clinical condition, other concomitant events). Although an AE may rate only as "possibly related" soon after discovery, it can be flagged as requiring more information and later be upgraded to "probably related" or "definitely related", as appropriate.
- Unlikely to be related A clinical event, including an abnormal laboratory test
 result, whose temporal relationship to study procedures administration makes a
 causal relationship improbable (e.g., the event did not occur within a reasonable
 time after administration of the study procedures) and in which other drugs or
 chemicals or underlying disease provides plausible explanations (e.g., the
 participant's clinical condition, other concomitant treatments).
- Not Related The AE is completely independent of study procedures administration, and/or evidence exists that the event is definitely related to another etiology. There must be an alternative, definitive etiology documented by the clinician.

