8.3.4 Time Period and frequency of Event Assessment and Follow-up

This retrospective study will only capture past self-reported vaginal infections. There will be no way to tell if it was a potentially related adverse event of the Mosie Kit use in a one time survey. No additional follow-up will be conducted. No identifying information will be collected to allow follow up.

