Analysis: Descriptive statistics will be used to analyze perceived safety. Qualitative analysis will be used on any comments made related to safety. Rates of vaginal infections will be analyzed using descriptive statistics.

Secondary Hypothesis 5: The majority of participants indicate they have little to no safety concerns related to using the Mosie Kit. Alternative hypothesis is the majority of participants will be very concerned or extremely concerned about the safety of using the Mosie Kit.

Analysis: Descriptive statistics of self-reported level of concern. Additionally, safety measures such as hand washing, disposing of the syringe after use, and reading the instructions will be examined using descriptive statistics.

Tertiary Hypothesis 1: There will be higher pregnancy rates when using the Mosie Kit when the source of infertility is male-based than when it is female-based. The alternative hypothesis is there will be lower pregnancy rates when using the Mosie Kit when the source of infertility is male-based than when it is female-based.

Analysis: In addition to the descriptive statistics a t-test will be run to examine this hypothesis.

Tertiary Hypothesis 2: There is a difference in pregnancy rates of people with known fertility issues depending on the source of their infertility. Specifically, the following sources of infertility will be examined if sufficient data is available.

- o PCOS
- Endometriosis
- Low AMH or low ovarian reserve
- Low sperm count
- Sperm motility issues
- Unexplained infertility
- Erectile dysfunction
- Performance issues or sexual anxiety, or inability to orgasm with partner.

Page 27

- Vaginismus or vulvodynia
- Tilted uterus
- Multiple uterus/cervix
- Loss of a fallopian tube

The alternative hypothesis is that there will be no difference in the fertility rates associated with different sources of infertility.

Analysis: Descriptive statistics, t-test, correlations and multiple ANOVAs will be used to examine this hypothesis.

Tertiary Hypothesis 3: There will be a difference between individuals who perform 2 insemination instances as described in the instructions and those that follow a different schedule or dosage number. The alternate hypothesis is that there will be no difference between the individuals that perform the minimum 2 insemination instances and those that follow difference dosage schedule.

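### The AE causality grading in 8.3.3.2 cannot be validly carried out on an anonymous one-time survey that, by 8.3.4, cannot tell relatedness; the 7-month infection recall can also reach back before kit use

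*Combined protocol and SAP*

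**What the plan says.** Section 8.3.3.2 covers all adverse events. Their relationship to study procedures, including the intervention, is to be "assessed by an appropriately-trained clinician based on temporal relationship"; clinical judgment is named as a second basis. It adds: "The degree of certainty about causality will be graded using the categories below". Five grades follow, from *Definitely Related* to *Not Related*. For the last it states: "There must be an alternative, definitive etiology documented by the clinician".

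Section 8.3.4 describes what will be available: "This retrospective study will only capture past self-reported vaginal infections". It continues: "There will be no way to tell if it was a potentially related adverse event of the Mosie Kit use in a one time survey". Follow-up is not planned and identifiers are not collected. Section 8.3.5 repeats that respondents who report events cannot be followed up. Section 10.1.9.1 says that nothing from outside will be joined to the survey data.

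Section 8.3 says that the survey asks about infections over the prior 7 months, that these may have nothing to do with the syringe, and that they will be expressed per respondent and per cycle. It also names finding adverse events caused by the kit as a study goal. For Secondary Hypothesis 4, section 9.1 plans: "Rates of vaginal infections will be analyzed using descriptive statistics".

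**The concern.** One section orders a causality grade for every event. The next-but-one section says that the judgment cannot be made, and uses almost the name of the scale's middle grade (*Potentially Related*) to say so. Nothing states which governs, so a reader cannot tell whether grading will happen.

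If grades were assigned and reported, they would look like clinical attribution without adequate evidence behind them. Perceived safety is a secondary endpoint, and section 10.1.3 allows aggregate results to be used in marketing, so the plan should say beforehand what may be claimed.

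The recall window raises a related problem that does not depend on grading. If infections are counted over a period that starts before some respondents had a kit, the descriptive rate is not a rate of infections after kit use, although section 8.3 links it to the search for events caused by the kit.

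**Working it through.** The plan gives no figure to reproduce here. The first step compares the text; the second is simple arithmetic on the windows.

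**Step 1: what each grade needs, against what the study can supply.**

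| Grade in 8.3.3.2 | Evidence it calls for | Available from the survey? |
|---|---|---|
| Definitely | Plausible timing, other causes ruled out, response to withdrawal | No means to rule out causes or observe withdrawal |
| Probably | Reasonable timing, other causes unlikely, response on withdrawal | Same |
| Potentially | Some evidence, such as timing; may be upgraded with more information | 8.3.4 says this cannot be told; no later information can arrive |
| Unlikely | Timing makes a causal link improbable, and another explanation is plausible | No clinical contact or records |
| Not related | Definitive alternative cause, documented by the clinician | No clinician contact, no records |

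The last column rests on 8.3.4, 8.3.5 and 10.1.9.1. In the legible part of Appendix A, the infection items cover type and what was done about it. None of the legible items dates the onset.

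**Step 2: recall window against purchase window.**

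Inputs: recall R = 7 months (8.3); time since purchase m = 2 to 8 months at study start (section 5). Assumptions: first use follows that purchase, and the survey is answered at study start with recall counted back from then.

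- Recall months before any possible use = max(0, R − m)
- Months of possible use outside recall = max(0, m − R)

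| m (months) | Recall months before purchase | Share of 7 | Possible use not covered |
|---|---|---|---|
| 2 | 7 − 2 = 5 | 71% | 0 |
| 3 | 4 | 57% | 0 |
| 4 | 3 | 43% | 0 |
| 5 | 2 | 29% | 0 |
| 6 | 1 | 14% | 0 |
| 7 | 0 | 0% | 0 |
| 8 | 0 | 0% | 8 − 7 = 1 |

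Someone who answers a month after study start has m larger by 1, so the most recent buyers move from 5 months to 4. If enrolment is extended, section 5 keeps a minimum of 2 full months between purchase and invitation, so 5 months remains the upper bound. It is smaller for anyone who already used an earlier kit, and larger if first use came some time after purchase.

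An undated infection from a recent buyer therefore cannot be placed before or after use. The effect on the overall rate cannot be computed, because the documents give neither the spread of purchase months nor an infection incidence.

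**The case against.** The strongest reply is that the study-specific text already controls. Section 8.3 says how infections will be handled before it introduces the definitions, 8.3.1 limits event data to what the participant provides, 8.3.4 disclaims relatedness, and 9.1 plans only descriptive rates. On this view 8.3.3.2 is generic text never adapted to a survey, and counting infections regardless of cause is already the plan.

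Most of this stands, and it is why the point is minor. It does not remove the conflict: 8.3.3.2 is mandatory and covers all events, 8.3 presents the classification as part of this protocol, and the goal of finding events caused by the kit remains.

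Several stronger readings are tempting and are not supported:

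- A reader might infer that the study will publish a split into related and unrelated infections. Section 9 plans no such table or test.
- A reader might infer that a grader could by default call every infection unrelated. A grader who followed 8.3.3.2 could not, because *Not Related* needs a documented alternative cause and *Unlikely* needs timing evidence plus another explanation.
- A reader might infer that there are no data at all on onset. Several survey pages are figures not shown, and the legible items do not show the 7-month wording that 8.3 describes, so an onset question cannot be excluded. The grading basis also includes clinical judgment, not timing alone.
- A reader might infer that perceived safety and infection rates are the whole safety output. Section 9.1 also plans level of concern, safety behaviours and analysis of safety comments.

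**Conclusion.** The contradiction is real: 8.3.3.2 requires a causality grade for every event, and 8.3.4, 8.3.5 and 10.1.9.1 together mean that it cannot be validly assigned. The consequence is conditional, since it arises only if grades are assigned and reported.

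The second part holds whether or not anyone grades. For the most recent buyers, up to 5 of the 7 recall months (71%) can precede purchase, assuming first use follows that purchase, so the planned infection rate can mix events before and after kit use. For buyers at 8 months, up to 1 month of possible use is missed.

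Severity is minor. The primary analysis is not touched, and the planned infection analysis is already descriptive.

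**What to change.** Reconcile 8.3, 8.3.3.2 and 8.3.4:

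- State in 8.3.3.2 that causality grading does not apply to survey-reported events.
- State in 8.3 and under Secondary Hypothesis 4 in 9.1 that all reported infections are counted and described regardless of relatedness, and that no related or unrelated statement will be made.
- Reword the goal in 8.3 so that it describes reported infections among kit users rather than events caused by the kit.
- Say when reporting the rate that the recall period may include time before kit use.

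This costs a few sentences and removes the need for a clinician grader.

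If the form does not already ask it and can still be changed, add one skip-logic item for those who report an infection: began before first kit use, after a kit insemination, or don't know. Report infection counts by that answer, without a causality grade. Appendix A allows questions to be revised and already uses skip logic; the change would need IRB approval. The documents do not show whether the form was already in use, so this part depends on that, while the text changes do not. The cost is one more question, answered from memory.
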